2.3 Correlative Studies Background

2.3.1 Elucidating the Pharmacodynamic Effect of Hydroxychloroquine and Itraconazole Combination on Tumour Cellular Metabolism: Impairment of cholesterol-trafficking.

Given that the cytotoxic effect of the combination therapy is thought to be mediated via the impairment of cholesterol-trafficking, we will focus on examining genes related to lipoprotein signaling and cholesterol transport, synthesis and metabolism. Tumour and blood samples (archival, pre- and on-treatment) will be obtained from women with advanced EOC.

To determine the biologic mechanisms underlying hydroxychloroquine and itraconazole, tumour biopsies obtained prior to and during treatment will be examined by FILIPIN staining. This will assist in determining accumulation of free cholesterol. Immunofluorescence (IF) assays will be employed to examine co-localization of free cholesterol with late endosomes/ lysosomes (LAMP1). IHC will also be employed to assess the presence of other related proteins including but not limited to NPC1, SCP2 and STARD3. NPC1 is a protein that is found to be aberrant in Neimann-Pick Type C disease which affects cholesterol trafficking. Recently, this same protein has been found to be inhibited by itraconazole causing a block in the cholesterol trafficking pathway and subsequent inhibition of mTOR [37]. SCP2 and STARD3 are thought to be two of the major proteins associated with cellular cholesterol trafficking. SCP2 is responsible for binding cytoplasmic cholesterol and transporting it to the plasma membrane. STARD3 is a transmembrane protein that is responsible for cholesterol efflux [13]. Free and esterified cholesterol will be assessed in pre- and on-treatment tumour tissue by Bodipy staining.

Whole mRNA sequencing will be done on RNA extracted from tumour tissue to determine whether a modification in certain transcripts affects the synthesis or uptake of cholesterol has occurred as a result of hydroxychloroquine and itraconazole.

In tandem, pre- and on-treatment blood will be analyzed colorimetric/flow cytometry to characterize/quantify free and esterified cholesterol accumulation.

We will examine the consequence of impairments in cholesterol trafficking in normal cells. Serum lipid levels will be monitored; and peripheral blood mononuclear cells will be evaluated for lipid accumulation.

2.3.2 Evaluate the Impact of Hydroxychloroquine and Itraconazole on Autophagy

Hydroxychloroquine has previously been shown to inhibit autophagy whereas itraconazole has been shown to do the opposite. Our pre-clinical studies have shown that hydroxychloroquine and itraconazole work synergistically to trap cholesterol in autophagolysosomes, thereby inducing the accumulation of toxic levels of cholesterol within the cell and causing cellular death.

To investigate the role of autophagy in this process, LC3B and p62, both proteins involved in autophagy will be investigated using IHC. Presence of both these proteins indicates a basal autophagy level and inhibition of autophagy will lead to decreased detection [38].

2.3.3 Evaluate Impact of Hydroxychloroquine and Itraconazole Combination Therapy on Proliferation and Apoptosis

To determine the extent to which autophagy contributes to the survival of EOC cells, and conversely, the extent to which inhibition of autophagy contributes to cell death, we will investigate dynamic changes in markers of cell proliferation or death. We examine this using IHC markers of apoptosis (e.g., caspase 3 cleavage products) and proliferation (e.g., ki67).

Gamma-H2AX, a marker of DNA damage, will also be assessed via IHC.

2.3.4 Evaluate Impact of hydroxychloroquine and Itraconazole Upon Angiogenesis in Platinum-resistant EOC

Angiogenesis seems to play an important role in the dissemination of EOC and anti-angiogenic agents such as bevacizumab have been shown to increase response rates to chemotherapy as well as prolong PFS and OS in a select patient population [39, 40]. Interestingly, the downregulation of autophagy has also been described to increase angiogenesis [41]. The interplay between anti-autophagy agents such as hydroxychloroquine and angiogenesis remain largely uninvestigated. However, itraconazole is thought to downregulate angiogenesis [6, 11, 15, 42], and thus, the combination of these specific agents may offer a solution to the escape mechanisms cancer cells may use to circumvent inhibition of autophagy. To investigate the impact of hydroxychloroquine and itraconazole therapy on angiogenesis, IHC will be performed on tumour tissue for CD31 as a marker of endothelial cells as well as HIF- 1α , which is induced by hypoxia and mediates VEGF activity and angiogenesis [43, 44]. Investigating the impact of this therapy on angiogenesis will help to further characterize the mechanism of action of the combination treatment.

2.3.5 Determine the Impact of Alterations in Genes and Gene Products Related to Cell Proliferation and Autophagy in Platinum-resistant EOC and Response to Combination hydroxychloroquine and Itraconazole Therapy

Canonical pathways such as PI3K-AKT and mTOR are often altered in cancer and contribute to resistance to therapy. These pathways serve to enhance nutrient uptake and macromolecule biosynthesis and support cellular proliferation. These have also been described to negatively regulate autophagy [45]. We will use next generation sequencing to study the impact of mutations in genes involved with cell metabolism and proliferation the PI3K - AKT and mTOR pathways.

2.3.6 Validation of Putative Biomarker Genes

Patient tissue will be used to create cell lines and investigate the effect of knocking out putative biomarker genes essential to autophagy and cholesterol trafficking using CRSPR/Cas 9 drop out screens. These screens will be used to prospectively validate these genes as important players in the mechanism of action of the combination therapy of hydroxychloroquine and itraconazole.

2.4 Impact on Cancer Care

Should the combination of hydroxychloroquine and itraconazole be found to be a safe, tolerable and demonstrate anti-cancer activity in vivo, this allows for a novel and cost-effective strategy for the treatment of chemotherapy-resistant EOC as well as potentially other chemotherapy-resistant cancers.

3. PATIENT SELECTION

3.1 Inclusion Criteria

- 3.1.1 Patients aged 18 years or older with histologically or cytologically confirmed epithelial ovarian cancer.
- 3.1.2 Platinum-resistant or refractory disease defined as a radiological or clinical progression less than six months after having finished platinum-based chemotherapy.
- 3.1.3 ECOG performance status equal to or less than 1.
- 3.1.4 Patients must have clinically or radiographically documented measurable disease. Radiographic measurable disease is defined as at least one site of disease that is unidimensionally measurable as follows [46]:

○ CT-scan, physical exam
 ○ Chest X-ray
 ○ Lymph node short axis
 ≥10 mm
 ≥20 mm
 ≥15 mm

- All radiology studies must be performed within 28 days prior to registration (35 days if negative).
- 3.1.5 All systemic therapy must have been completed ≥ 4 weeks prior to enrollment with radiologic evidence of disease progression.
- 3.1.6 Life expectancy should be more than 3 months.
- 3.1.7 Patients receiving any medications or substances that are inhibitors or inducers of CYP3A4 are ineligible. Because the lists of these agents are constantly changing, it is important to regularly consult a frequently-updated list such as http://medicine.iupui.edu/clinpharm/ddis/table.aspx; medical reference texts such as the Physicians' Desk Reference may also provide this information.
- 3.1.8 Laboratory Requirements within 7 days prior to enrollment:

Haematology: hemoglobin ≥90 g/L

 $\begin{array}{ll} absolute \ neutrophils & \geq 1.5 \times 10^9/L \\ platelets & \geq 100 \times 10^9/L \end{array}$

Biochemistry: bilirubin within normal limits

AST(SGOT) $\leq 2.5 \times \text{institutional upper limit of normal}$

/ALT(SGPT)

serum creatinine within normal limits

or

creatinine clearance ≥60 mL/min/1.73 m² for patients with creatinine levels

above institutional normal

- 3.1.9 Subjects with treated and asymptomatic brain metastases are eligible. Patients that received palliative radiation (for brain metastases) are eligible if they have been asymptomatic for at least 2 weeks with use of maintenance steroid therapy, and last received radiation at least 4 weeks prior to start of therapy.
- 3.1.10 Patients must have the ability to understand and willing to sign a written informed consent document.

3.2 Exclusion Criteria

- 3.2.1 Patients who have not recovered (≤ grade 1) from adverse events related to previous treatments are excluded with the exception of alopecia and lymphopenia. Peripheral sensory neuropathy must be at grade 2 or less.
- 3.2.2 Patients with any other prior malignancy from which the patient has been disease free for less than 3 years, with the exception of adequately treated and cured basal or squamous cell skin cancer, superficial bladder cancer, carcinoma in situ of any site or any other cancer.
- 3.2.3 Patients with a history of allergic reactions attributed to compounds of similar chemical or biologic composition to itraconazole or hydroxychloroquine.
- 3.2.4 Patients with a known G6PD deficiency due to the risk of hemolytic anemia with the use of hydroxychloroquine.
- 3.2.5 Patients with known retinopathy due to the risk of worsening retinopathy with hydroxychloroquine.
- 3.2.6 Uncontrolled intercurrent illness including, but not limited to, ongoing or active infection, symptomatic or asymptomatic congestive heart failure, unstable angina pectoris, cardiac arrhythmia, or psychiatric illness/social situations that would limit compliance with study requirements. Patients with previous history of cardiac failure are excluded.
- 3.2.7 Patients on treatment with statin that cannot be interrupted for the duration of the study.
- 3.2.8 Patients with chronic Hepatitis B or hepatitis C infections should be excluded because of potential effects on hepatic function and/ or drug interactions.

- 3.2.9 Patients with known Human Immunodeficiency Virus (HIV) infection.
- 3.2.10 Patients with intestinal malabsorption or active bowel obstruction.
- 3.2.11 Patients who already have a clinical indication for treatment with itraconazole (e.g. chronic candidiasis or other fungal infection) or hydroxychloroquine (e.g. lupus).

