4.2 Registration Process

Prior to registering a patient, each institution must have submitted all necessary regulatory documentation to the Drug Development Program Central Office. The registration checklist will only be sent once this has been received.

No patient can receive protocol treatment until registration with the Central Office has taken place. All eligibility criteria must be met at the time of registration. There will be no exceptions. Any questions should be addressed with the Central Office prior to registration.

To register a patient, the following documents are to be completed by the research nurse or data manager and sent / faxed to the Central Office Study Coordinator:

- Signed patient consent form
- Registration Checklist signed by the investigator

To complete the registration process, central office will review the checklist and once eligibility has been confirmed:

- Assign a patient study number
- Assign the patient a dose
- Register the patient on the study
- Fax or e-mail the confirmation worksheet with the patient study number and dose to the participating site

To ensure immediate attention is given to the faxed checklist, each site is advised to also call the study coordinator listed on the front sheet. Patient registration will be accepted between the hours of 9am to 5pm Monday to Friday, excluding Canadian statutory holidays when the central office will be closed.

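### The prior-malignancy exclusion (3.2.2) ends its exceptions with a catch-all, so its 3-year disease-free limit largely loses its function

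*Protocol*

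**What the plan says.** Protocol section 3.2.2 opens with a time-limited exclusion: "Patients with any other prior malignancy from which the patient has been disease free for less than 3 years". It then lists exceptions, beginning "with the exception of adequately treated and cured basal or squamous cell skin cancer" and ending "superficial bladder cancer, carcinoma in situ of any site or any other cancer". The main exclusion criteria in the synopsis carry the same sentence, so neither place corrects the other.

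On how the criteria are applied, section 4.2 says: "All eligibility criteria must be met at the time of registration. There will be no exceptions". The same section sends eligibility questions to the Central Office before registration, and that office confirms eligibility from the checklist.

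**The concern.** An exception list works by being closed: it names the cancers considered harmless enough to ignore and leaves the rule to cover the rest. Here the last item is open-ended. It carries no site, stage or time limit, so it reaches the very cancers that the first half of the sentence sets out to exclude.

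What is at stake is how lesions are attributed in the two secondary efficacy endpoints. Response rests on RECIST measurements, and any new lesion counts as progression (section 11.1.4). In a patient with a recent second invasive cancer, a lesion from that cancer could be measured as ovarian disease or counted as a new ovarian lesion. The paired biopsies could be affected in the same way. The analysis rules do not remove such a patient later. Section 13.5.2 bases conclusions on all eligible patients and does not let subanalyses that exclude patients support efficacy conclusions. A patient admitted under the exception is eligible, and so stays in.

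**Working it through.** The protocol gives no figure to reproduce on this point. The check is of wording, with one small piece of arithmetic at the end.

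**Step 1: is the sentence intact?** It reads the same, complete, in section 3.2.2 and in the synopsis. A break in text extraction or a redaction is therefore not the explanation.

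**Step 2: test the possible readings.**

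| Reading | Who is exempt | What is left of the 3-year limit |
|---|---|---|
| A. The qualifier covers only the skin cancers, and the closing phrase stands alone | Every other cancer, treated or not | Nothing: the criterion excludes nobody |
| B. The treated-and-cured qualifier governs the whole list | Any second cancer judged cured, however recent | It applies only to patients who are disease free but not judged cured |
| C. The closing phrase belongs to carcinoma in situ | In-situ disease of any other cancer | The limit would work, but the reading is strained because in-situ disease of any site is already named |

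Under A and B the named low-risk cancers become redundant, which points to a drafting slip. Under B the test that decides most cases is whether the second cancer is cured. The protocol does not define that term, so site judgement replaces a dated criterion. For comparison, the exceptions in 3.2.1 to recovery from earlier adverse events are a closed list.

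**Step 3: does anything else restore the limit?**

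- 3.1.1 requires confirmed epithelial ovarian cancer but does not bar a second cancer.
- 3.1.5 requires at least 4 weeks since systemic therapy, with radiologic progression. It says nothing about how long a second cancer has been absent.
- 3.2.6 concerns uncontrolled intercurrent illness.
- 4.2 rules out waivers. It gives the Central Office no stated ground for refusing a patient whom 3.2.2 exempts.

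None of these restates a 3-year interval.

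**Step 4: size per patient.** Inputs from section 13.2: 9 response-evaluable patients in stage 1 and 25 more in stage 2.

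- Final denominator: 9 + 25 = 34.
- One patient's weight in the response rate: 1/34 = 0.029, or 2.9 percentage points.
- Stage 1 stops only at 0 responses in 9. If the true count were 0, one misread response would carry the trial into stage 2.

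How many patients would be admitted through the exception, and how many of those would be misread, cannot be computed from the protocol.

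**The case against.** The case on the other side is substantial on consequences, less so on the wording.

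- **Reading B is the natural one.** An investigator is unlikely to apply reading A, which makes the named cancers pointless. Under B, active second cancers and treated cancers not judged cured remain excluded. This stands. A reader might infer that the criterion excludes no treated second cancer at all, but the text supports that only under A.
- **Regressing lesions.** A lesion still shrinking after treatment of another cancer is residual disease, which is hard to call cured. That scenario essentially needs reading A, and 3.1.5 limits carry-over from systemic therapy, though not from surgery or radiotherapy.
- **Deaths.** A reader might add deaths from the second cancer to the misattribution problem. Section 11.1.6 counts death without regard to cause, so such a death is a progression-free survival event by definition. The concern is confined to lesions.
- **Safeguards.** Section 11.1 asks for a confirmatory scan at least 4 weeks after a response, and 11.1.8 provides central radiology review. Both reduce spurious calls, but neither establishes tumour origin.
- **Stage 1.** A reader might conclude that one foreign lesion would decide the interim look. Response is judged on the sum of all target lesions, so one lesion suffices only if it dominates that sum.
- **Checklist.** A reader might assume that the registration checklist carries the same error. It is not part of the document, so this is unknown. Questions can also go to the Central Office before registration, although nothing in the protocol tells that office which reading to adopt.

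These points narrow the consequences. None of them makes the 3-year limit work as its first half intends.

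**Conclusion.** The criterion is wrong as written, in two places. It either excludes nobody or hands most of the decision to an undefined judgement of cure. Under both readings a recent second invasive cancer can be eligible.

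The effect is limited. The primary endpoint, the maximum tolerated dose and recommended phase II dose, does not depend on it, and neither do the Simon design calculations. Response rate and progression-free survival are secondary, and the exposure is 2.9 percentage points of response rate for each patient misclassified among 34. The number of such patients is probably small. Any prevalence of recent second cancers would be an outside assumption, and a patient admitted is not yet a patient misclassified.

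The conclusion rests on the wording alone and needs no assumption about prevalence. It does not rest on knowing which cancers the sponsor meant to exempt, which the text does not reveal. The defect is a cheap one to correct, worth correcting, and not a threat to the trial as a whole.

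**What to change.** The sponsor should state the intended scope of the exception and make section 3.2.2 and the synopsis agree. Two edits are available, and both use only what the protocol already contains:

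1. If only the named low-risk cancers are meant, delete the closing catch-all from the list of exceptions.
2. If the catch-all is a truncated restatement of the rule, complete it with the protocol's own limit, so that it covers other cancers only after a disease-free interval of at least 3 years.

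The registration checklist should then be checked against the corrected wording.

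The cost is one clause in the next amendment. The downside is that a few candidates with a recent second cancer are screened out, which the first half of the criterion already intends.

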3.3 Pregnancy

Both itraconazole and hydroxychloroquine are contraindicated in pregnancy. Due to potential teratogenic effects, women of child-bearing potential must agree to use adequate contraception (hormonal or barrier method of birth control; abstinence) prior to study entry and for the duration of study participation. Should a woman become pregnant or suspect she is pregnant while she or her partner is participating in this study, she should inform her treating physician immediately.

3.4 Inclusion of Women and Minorities

Women of all races and ethnic groups are eligible for this trial. This study is designed to include minorities as appropriate. However, the trial is not designed to measure differences in intervention effects. The population of Southern Ontario is ethnically diverse and the proportion of different ethnic groups in the community is provided in the table below. Universal access to health care will ensure that there is no discrimination on the basis of race or gender (Guide to Canadian Human Rights Act: www.chrc-ccdp.ca/public/guidechra.pdf). Individual hospital registries and databases do not routinely collect racial data, under the direction of the Canadian Human Rights Code.

4. REGISTRATION PROCEDURES

4.1 General Guidelines

The Study Coordinator at the Princess Margaret Hospital Consortium Central Office will enter eligible patients on study centrally. The required forms (Registration Checklist) will be provided upon site activation.

Following registration, patients should begin protocol treatment within 72 hours. Issues that would cause treatment delays should be discussed with the Principal Investigator (cc the central office study coordinator). If a patient does not receive protocol therapy following registration, the patient's registration on the study may be cancelled. The Study Coordinator should be notified of cancellations as soon as possible.

4.2 Registration Process

Prior to registering a patient, each institution must have submitted all necessary regulatory documentation to the Drug Development Program Central Office. The registration checklist will only be sent once this has been received.

No patient can receive protocol treatment until registration with the Central Office has taken place. All eligibility criteria must be met at the time of registration. There will be no exceptions. Any questions should be addressed with the Central Office prior to registration.

To register a patient, the following documents are to be completed by the research nurse or data manager and sent / faxed to the Central Office Study Coordinator:

- Signed patient consent form
- Registration Checklist signed by the investigator

To complete the registration process, central office will review the checklist and once eligibility has been confirmed:

- Assign a patient study number
- Assign the patient a dose
- Register the patient on the study
- Fax or e-mail the confirmation worksheet with the patient study number and dose to the participating site

To ensure immediate attention is given to the faxed checklist, each site is advised to also call the study coordinator listed on the front sheet. Patient registration will be accepted between the hours of 9am to 5pm Monday to Friday, excluding Canadian statutory holidays when the central office will be closed.

5. TREATMENT PLAN

5.1 Agent Administration

Treatment will be administered on an outpatient basis. Reported adverse events and potential risks are described in Section 7. Appropriate dose modifications are described in section 6. No investigational or commercial agents or therapies other than those described below may be administered with the intent to treat the patient's malignancy.

The patient will be requested to maintain a medication diary of each dose of medication. The medication diary will be returned to clinic staff at the end of each course.

Regimen Description					
Agent	Premedications / Precautions	Dose	Route	Schedule	Cycle Length
itraconazole	Take with food	300 mg	PO	twice daily	
hydroxychloroquine	Take with food or milk Antacids should not be taken within 4 hours before or 4 hours after dosing with hydroxychloroq uine	** tablet	PO	** once or twice daily	28 days (4 weeks)
**Doses as appropria	te for assigned dose	e level.	1	1	

